9.4 STATISTICAL ANALYSES

9.4.1 General Approach

Analysis will be performed by a statistician from the Data Coordinating Center using SAS® software (version 9.4 or updated version).

Continuous variables will be summarized using descriptive statistics, i.e. number of subjects, mean, standard deviation (SD), median, inter quartile range, minimum and maximum depending on the variable distribution. Categorical variables will be summarized by frequency and percentage.

The statistical analysis plan (SAP) will include a more technical and detailed description of the statistical analyses described in this section. It will be written before data base lock. In case of occurrence of such validated modifications after the SAP, a modified SAP would be issued. The original SAP as well as the modified SAP will be kept in the study files, with the justification for any modification. The SAP will prevail in case of any differences with planned analyses described in this protocol.

9.4.2 Analysis of the Primary Efficacy Endpoint(s)

The primary endpoint of change in CRP level (CRP level measured at inclusion, day 2, day 4, day 7, and day 31) will be compared between treatment groups using an appropriate contrast at day 7 from a mixed model for repeated measures (MMRM) of post-inclusion changes in CRP that includes the effects of center, baseline CRP, treatment, visit, baseline CRP×visit and treatment×visit. CRP values will be log-transformed for analysis. Patients' available measures will be included in the model with no imputation for missing values. MMRM with a contrast may provide more power than a complete-case ANCOVA, and should include baseline covariates×time interactions to minimize bias.

9.4.3 Analysis of the Secondary Endpoint(s)

Treatment groups will be compared with respect to the occurrence of a WHF adverse event, or HF readmission, or death from any cause from randomization through day 91 with a log-rank test stratified by study center. The time to event will be calculated as the date of the first occurrence of any of the component events minus the date of randomization plus 1. If a patient has no component event by day 91, the time to event will be censored at the earlier of 90 days after randomization or the day of last available follow-up.

The changes in EQ-5D-5L index value and in EQ-VAS from randomization to day 7, will be compared between treatment groups using an appropriate contrast at day 7 from a mixed model for repeated measures (MMRM) for each outcome that includes the effects of the baseline value (EQ-5D-5L index or EQ-VAS as applicable), study center, treatment, visit, baseline value×visit and treatment×visit. EQ-5D index will be derived for each patient from the French value set. Patients who are missing a response due to death will be assigned the index value equivalent to death (0) and worst possible VAS score (0). The method assumes that missing data are missing at random (MAR) and the hypothetical treatment effect that is estimated is what would have been observed if all patients had continued on the assigned treatments for the full treatment period. Shifts in responses to each dimension from baseline to each time point will also be described.

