6.5.3 Rescue Medicine

Aside from the study treatment, the management of the patient is at the discretion of the treating physician. If there is a formal indication for further steroid therapy, the prednisone treatment can be given in the control group and recorded in the CRF, and in both groups even after day 7. All treatments necessary for the proper management of the patient's state in the ED/hospital and subsequent hospitalization are authorized.

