7 STUDY INTERVENTION DISCONTINUATION AND PARTICIPANT DISCONTINUATION/WITHDRAWAL

7.1 DISCONTINUATION OF STUDY INTERVENTION

Several situations are possible:

- Temporary suspension of treatment: the investigator must document the reason for suspending and resuming the treatment in the participant's source file and the case report form (CRF)
- Premature discontinuation of treatment, but the participant remains enrolled in the study until the end of their participation
- Premature discontinuation of treatment and withdrawal from the study
- If, during the course of his/her participation in the study, the participant presents one of the following criteria, then the study treatment must be discontinued but the participant will continue to be monitored for the study.
 - Thrombo-embolism event
 - Fracture
 - Gastro-intestinal bleeding
 - altered consciousness, confusion or dementia, psychotic state,
 - vaccination, hypersensitivity reaction,
 - pregnancy, severe renal or hepatic impairment, or
 - uncontrolled hyperglycemia.

The investigator must:

- Document the reason(s)
- Collect the assessment criteria at the time of ending participation in the study, if the participant agrees
- Schedule a follow-up for the participant, particularly in case of a serious adverse event.

In the case of severe adverse events, the investigator must notify the sponsor and follow up the participant for 1 month following the premature discontinuation of treatment. The Sponsor will be notified immediately of any serious adverse event. The serious adverse event will be monitored until it is resolved.

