8.1.8 EQ-5D-5L questionnaire

The EQ-5D is a standardized instrument developed by the EuroQoL Group (www.euroqol.org) that measures health-related quality of life (The Euroqol Group 1990). The EQ-5D consists of two pages, which should take only a few minutes to complete (Oppe, Rabin et al. 2008). The first page asks the patient to indicate his/her health state for each of 5 dimensions (mobility, self-care, usual activities, pain/discomfort and anxiety/depression). The second page asks the patient to rate his/her health on a vertical visual analogue scale (EQ-VAS), where the endpoints are labeled “Best imaginable health state” at the top and “Worst imaginable health state” at the bottom. The 5-level EQ-5D version (EQ-5D-5L), introduced in 2009, increased the number of possible response levels to each health dimension from 3 to 5.

The patient will be asked to complete the EQ-5D-5L questionnaire at Visits 1 (randomization), Visit 4 (day 7), and Visit 5 (30 days post-randomization) in a quiet, private space prior to any invasive or demanding study or routine procedures, e.g., blood draws, by using the official linguistically validated translation of the EQ-5D-5L. See appendix in section 12.1 for sample English version (not to be used in the study).

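### The EQ-5D analysis scores deaths as 0 but is described as estimating the effect had all patients continued treatment; the death scores make it composite for death

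*Protocol*

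**What the plan says.** Protocol 9.4.3 compares the change in EQ-5D-5L index and in EQ-VAS from randomization to day 7, using a day 7 contrast from a mixed model for repeated measures (MMRM). Three statements in that paragraph matter here.

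- Deaths: "Patients who are missing a response due to death will be assigned the index value equivalent to death (0"), and the VAS is likewise set to its worst score, 0.
- Missing data: "The method assumes that missing data are missing at random (MAR").
- Interpretation: the "hypothetical treatment effect that is estimated is what would have been observed if all patients had continued on the assigned treatments" over the full treatment period.

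Other sections bear on how this reads.

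- 8.1.8 sets the questionnaire times: "The patient will be asked to complete the EQ-5D-5L questionnaire at Visits 1 (randomization), Visit 4 (day 7), and Visit 5" at 30 days.
- 7.1 lists events after which "then the study treatment must be discontinued but the participant will continue to be monitored for the study".
- 6.5.3 allows steroid outside the allocation: "the prednisone treatment can be given in the control group and recorded in the CRF, and in both groups even after day 7".
- 9.3 makes the per-protocol set the population for the main analysis. It excludes patients for whom eligibility or the allocated treatment was not respected, and it promises an intention-to-treat sensitivity analysis for the main endpoint only.

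**The concern.** The interpretation sentence claims a purely hypothetical effect: quality of life as it would have been if nobody had left assigned treatment. The death rule two sentences before it does something else, because it makes death the worst possible quality-of-life result. That is a composite strategy, and a reasonable one, but it answers a different question.

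What is at stake is what the EQ-5D result can be said to show. If the report carries the protocol's sentence forward, a difference that comes partly or wholly from deaths would be described as an effect on quality of life under continued treatment. In a pilot trial of this size a few deaths in one arm are enough for that to matter to the interpretation.

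**Working it through.** **Consistency of the statements in 9.4.3**

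1. Take a patient who dies on day 3. Under the death rule, the day 7 index and VAS are both 0, and the change entering the model is 0 minus the baseline value.
2. Because a value has been assigned, nothing is missing for that patient at day 7. The missing-at-random assumption therefore does not apply to deaths. It covers only the other missing responses.
3. The patient did not continue for the full treatment period, and 0 is not an estimate of what continued treatment would have given. The contrast therefore contains a value that the interpretation sentence rules out.
4. The reference to all patients also does not match 9.3, where the main analysis leaves out patients with major deviations.

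**Size**

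The Protocol gives no power or sample-size figure for EQ-5D. Its only design figure, about 80% power for CRP with 60 per arm (9.2), reproduces: |ln 0.6| = 0.511 and SD 1.002 give 79.7% by the normal approximation and 79.1% by the noncentral t with 118 df. This point does not affect it.

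Inputs:
- 60 patients per arm (9.2).
- One-month mortality of 6% overall and up to 10% at age 75 and over (2.3.2).
- Assumptions, not in the Protocol: constant hazard over 30 days; mean score if alive of 50 to 75 for VAS and 0.6 to 0.8 for the index.

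Deaths by day 7, from q = 1 − (1 − m)^(7/30):
- m = 0.06: q = 0.0143, so 60 × 0.0143 = 0.86 per arm (1.72 in 120).
- m = 0.10: q = 0.0243, so 60 × 0.0243 = 1.46 per arm (2.91 in 120).

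Shift in the arm difference per excess death = mean if alive / 60:

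| Score | Assumed mean if alive | Shift per excess death |
|---|---|---|
| VAS | 50 | 50/60 = 0.83 |
| VAS | 75 | 75/60 = 1.25 |
| Index | 0.6 | 0.6/60 = 0.010 |
| Index | 0.8 | 0.8/60 = 0.013 |

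For scale, assume an index mean of 0.7 and SD of 0.20 among survivors. One death in 60 (q = 1/60) raises that arm's SD to √[(1 − q)·0.20² + q(1 − q)·0.7²] = 0.218. The standard error of the arm difference, before baseline adjustment, is √[(0.218² + 0.20²)/60] = 0.038. The shift of 0.7/60 = 0.0117 is then about 0.3 of a standard error.

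For the exploratory day 31 change, the same mortality gives 60 × 0.06 = 3.6 to 60 × 0.10 = 6 deaths per arm, so there is more room for an imbalance.

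**The case against.** The strongest defence is that the death rule is stated openly in the same paragraph, and that a composite strategy for death combined with a hypothetical strategy for stopping treatment can be a coherent estimand. On that reading the interpretation sentence concerns only the remaining missing data. Deaths are also analysed separately to days 31 and 91 (9.4.9), so a reader of the report could see them. This argument shows that the analysis itself is legitimate. It does not rescue the sentence, which speaks of all patients and makes no exception for death. A later SAP prevails over the Protocol (9.4.1), but the sentence is a misstatement in the Protocol, not a detail left open.

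A reader might go further and infer that the result is really a treatment-policy effect, because patients who stop are still followed ("Premature discontinuation of treatment, but the participant remains enrolled in the study until the end of their participation") and because "the prednisone treatment can be given in the control group and recorded in the CRF". The documents do not support that.

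- They say that follow-up continues and that steroid use is recorded. They do not say that EQ-5D values after stopping or after other steroid use enter the model. Such values can be collected and then set to missing, and that choice may properly sit in the SAP.
- The per-protocol set may remove some of these patients. 9.3 does not say whether stopping for a listed event, or permitted steroid use, counts as not respecting the allocated treatment.
- Steroid given after day 7 cannot change a day 7 response.

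A reader might also size the problem from one-month mortality, with all of one arm's 3.6 expected deaths set against none in the other. That uses a day 31 figure for a day 7 endpoint, together with an extreme split.

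**Conclusion.** The point holds for deaths. The EQ-5D analysis in 9.4.3 is composite for death, the missing-at-random assumption covers only the other missing values, and the sentence describing the effect as that of continued treatment in all patients is wrong as written. Whether values after stopping or other steroid use are kept cannot be settled from the Protocol and forms no part of this conclusion.

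This is mainly a matter of interpretation. At day 7 about one death per arm is expected, and a one-death imbalance moves the difference by roughly 1 VAS point or 0.01 index. Those figures rest on a constant hazard, on the Protocol's background mortality applying to this population, on the assumed mean scores, and on 60 analysed per arm. A smaller per-protocol set would give each death slightly more weight. The primary endpoint and the sample size are unaffected. The correction is still worth making, because it changes what a named secondary result can be said to show.

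**What to change.** Replace the interpretation sentence in 9.4.3 with wording such as:

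> Death is handled as part of the outcome (index 0, VAS 0); other missing values are assumed MAR, and the effect is estimated in the per-protocol population.

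If wording about continued treatment is kept, limit it to non-fatal discontinuation, and use it only if EQ-5D values after stopping study drug or after other steroid use are set to missing. Do not label the effect treatment-policy while the per-protocol set is the main population.

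Add one sensitivity MMRM for index and for VAS without the death scores, reported beside the main result with the number of deaths per arm by day 7 and day 31. A difference driven by deaths would then be visible.

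The cost is a sentence and one extra model run per outcome. The sensitivity result has its own limit. A patient who dies before day 7 has no EQ-5D response after baseline, so without the death score that patient contributes nothing to the contrast, and the result conditions on survival. It should support the reading of the main result, not replace it.

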9.4.4 Safety Analyses

Adverse events will be coded using the Medical Dictionary for Regulatory Activities (MedDRA). The incidence of adverse events with an onset after randomization through 30 days post-randomization will be tabulated by system organ class and preferred term. All adverse events, fatal adverse events, serious adverse events will be summarized by treatment group. Treatment-related adverse events are those that are considered by the investigator as potentially, probably, or definitely related to the study intervention.

9.4.5 Baseline Descriptive Statistics

A flow chart will be drawn according to CONSORT statement. Baseline characteristics of patients will be described overall and per group.

9.4.6 Planned Interim Analyses

No interim analysis is planned. The study will be terminated after all patients have been enrolled and followed according to the protocol assessments. Analysis will be performed at the end of the study after data review and data base lock.

9.4.7 Sub-Group Analyses

Although power to detect significant interactions may be limited, analyses examining the treatment effect on the primary and secondary endpoints by subgroups based on baseline characteristics will be performed for the following factors:

- Sex: male versus female
- Age: < 65 versus \geq 65 years
- Baseline IL-6 : \leq 13 pg/mL versus IL-6 > 13 pg/mL

9.4.8 Tabulation of Individual participant Data

No tabulation of individual participant data is planned.

9.4.9 Exploratory Analyses

The following exploratory endpoints will be assessed:

1. The composite of WHF, death, or hospital readmission for decompensated HF at day 31, where WHF is defined as worsening signs and/or symptoms of HF that require an intensification of intravenous therapy (including initiation or re-initiation or dose increase) for HF or mechanical ventilatory, renal or circulatory support (occurring between 24 hours after randomization and the earlier of discharge or day 7).
2. The composite of WHF, death, or hospital readmission for decompensated HF at day 91, where WHF is defined as worsening signs and/or symptoms of HF that require an intensification of intravenous therapy (including initiation or re-initiation or dose increase) for HF or mechanical ventilatory, renal or circulatory support (occurring between 24 hours after randomization and the earlier of discharge or day 7).
3. Changes in quality of life measured by the EQ-5D-5L from randomization to day 31.
4. Changes from randomization to day 7 in NYHA classification, orthopnea, peripheral edema, rales, jugular venous pulse, and body weight.
5. Death from any cause to days 31 and 91.
6. Readmission for HF or death to days 31 and 91.
7. HF readmission through days 31 and 91.
8. Requirement for treatment with intravenous vasopressors, inotropes, and/or mechanical ventilatory, renal or circulatory support or death from randomization through day 7 (“treatment failure”).
9. Changes from randomization to day 7 and to day 31, in biomarker levels including brain natriuretic peptide (BNP), NT-pro-BNP, creatinine and troponin.
10. Time to worsening heart failure through the earlier of day 7 or discharge.
11. Length of stay in ICU through 30 days following randomization

12. Length of initial hospitalization through 30 days following randomization
13. Days dead or in acute care (including all intensive acute care units) out of the first 30 days following randomization.
14. Days dead or in the hospital out of the first 30 days following randomization.
15. Hospital re-admission through days 31 and 91.

10 SUPPORTING DOCUMENTATION AND OPERATIONAL CONSIDERATIONS

10.1 REGULATORY, ETHICAL, AND STUDY OVERSIGHT CONSIDERATIONS

10.1.1 Informed Consent Process

10.1.1.1 Consent/Assent and Other Informational Documents Provided to Participants

Consent forms describing in detail the study intervention, study procedures, and risks will be given to the participant and written documentation of informed consent is required prior to starting intervention/administering study intervention.

10.1.1.2 Consent Procedures and Documentation

No interventional research involving human participants can be carried out on a person without his/her freely given and informed consent, obtained in writing after the person has been given the information specified in ICH E6 Guideline for Good Clinical Practice.

A reflection period if needed is given to the individual between the time when he or she is informed and when he or she signs the consent form.

The person's freely-given, written, informed consent will be obtained by the principal investigator or a physician representing the investigator before the person is enrolled in the study.

A copy of the information note and consent form, signed and dated by the research participant and by the principal investigator or the physician representing the investigator will be given to the individual prior to their participation in the study. The principal investigator or the physician representing him/her will keep a copy.

At the end of the study, one copy will be placed in a tamper-proof sealed envelope containing all the consent forms. This envelope will be archived by the sponsor.

In addition, the investigator will specify in the person's medical file the person's participation in the research, the procedures for obtaining his/her consent as well as the methods used for providing information for the purpose of collecting it. The investigator will retain one copy of the signed and dated consent form.

The participant may not enroll in another interventional study protocol involving human participants for the duration of his or her participation without consulting with the physician monitoring him or her in the context of the study. The participants can, however, participate in other non-interventional studies.

10.1.2 Study Discontinuation and Closure

The Sponsor can prematurely discontinue all or part of the study, temporarily or permanently, further to the recommendations of the Medical Monitor if suspected unexpected serious adverse reactions (SUSARs) are observed in one of the treatment arms or if there is a discrepancy in the serious adverse reactions between the treatment arms, requiring a reassessment of the benefit-risk ratio for the study.

Similarly, the Sponsor or the Competent Authority may decide to prematurely discontinue the study due to unforeseen issues or new information about the product, in light of which the objectives of the study or clinical program are unlikely to be achieved.

The Sponsor reserves the right to permanently suspend enrolment at any time if it appears that the inclusion objectives are not met.

Patients already enrolled in the study at the time the study is prematurely discontinued will complete all study assessments through Day 91 as set forth in the protocol.

If the study is prematurely discontinued for safety reasons, the decision and justification will be provided by the sponsor to the Competent Authority and to the Ethics Committees within a period of 15 days.

10.1.3 Confidentiality and Privacy

Participant confidentiality and privacy is strictly held in trust by the participating investigators, their staff, and the sponsor(s) and their designates. This confidentiality is extended to cover testing of biological samples in addition to the clinical information relating to participants. Therefore, the study protocol, documentation, data, and all other information generated will be held in strict confidence. No information concerning the study or the data will be released to any unauthorized third party without prior written approval of the sponsor.

All research activities will be conducted in as private a setting as possible.

The study monitor, other authorized representatives of the sponsor, representatives of the Ethics Committee (EC), regulatory agencies may inspect all documents and records required to be maintained by the investigator, including but not limited to, medical records (office, clinic, or hospital) and pharmacy records for the participants in this study. The clinical study site will permit access to such records.

The study participant's contact information will be securely stored at each clinical site for internal use during the study. At the end of the study, all records will continue to be kept in a secure location for as long a period as dictated by the reviewing EC, Institutional policies, or sponsor requirements.

Study participant research data, which is for purposes of statistical analysis and scientific reporting, will be transmitted to and stored at the Data Coordinating Center at Momentum Research, Inc. This will not include the participant's contact or identifying information. Rather, individual participants and their research data will be identified by a unique study identification number. The study data entry and study management systems used by clinical sites and by the Data Coordinating Center research staff will be secured and password protected. At the end of the study, all study databases will be de-identified and archived at the Data Coordinating Center.

